1.0 Objectives

1.1 Study Objectives

The specific aims of the current study are to:

1) Examine the longitudinal effect of very low nicotine content (VLNC) cigarettes on changes in task-related functional neural activation within brain circuitry associated with incentive salience valuation and executive function. We hypothesize that, for the VLNC group compared to the normal nicotine content (NNC) group:

- a. Reactivity to smoking vs. pleasant odors within incentive salience circuitry will decrease.
- b. Reactivity to monetary rewards within incentive salience circuitry will increase.
- c. Activity during decision-making and inhibitory control within executive control circuitry will increase.

2) Assess the longitudinal effect of VLNC cigarettes on changes in effective (directional) connectivity between incentive salience and executive control brain circuitry. We hypothesize that, for the VLNC group compared to the NNC group:

- a. The influence of executive control over incentive salience circuitry, measured during task demands that simultaneously engage both processes, will increase.
- b. The influence of non-smoking reward salience circuitry over smoking salience circuitry during the odor cue reactivity task will increase.

3) Establish measurable and objective neural outcomes of successful reductions in smoking dependence.

1. We hypothesize that changes in functional activation and effective connectivity over the course of the VLNC intervention will be correlated with reductions in subjective and behavioral assessments of smoking dependence, including the number of cigarettes smoked per day, subjective reports of dependence, craving, and withdrawal.

4) Assess the effect of VLN Cigarettes vs NNC cigarettes on the levels of salivary miRNAs targeting dopamine, glutamate, acetylcholine and GABA-related transcripts over 6-weeks.

1. We hypothesize that the VLNC group will have significantly more changes in miRNA expression than the NNC group. A two-way repeated measures ANOVA will be conducted to compare changes in miRNA expression over three time points for the VLNC and NNC groups.

5) Determine if within-subject changes in miRNA expression are associated with changes in fMRI BOLD signal during smoking cue-reactivity and inhibitory control tasks for the VLNC group over 6-weeks.

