We currently know little about how neural activity and connectivity of the incentive salience and executive control circuitry change during recovery. Given the advancements in pharmacotherapy and non-invasive brain stimulation techniques,^{30,31} gaining a nuanced understanding of how brain circuitry adapts during rehabilitation could identify neural targets for treatment. VLNC cigarettes have been used as an extinction-based cessation treatment to reduce the rewarding effects of cigarettes by significantly reducing nicotine delivery during smoking.^{6,34} Over the course of a VLNC extinction trial with nicotine replacement therapy, smokers' reactivity in the amygdala to smoking over neutral visual cues decreased.³⁴ Participants who successfully abstained in a quit attempt following the extinction trial had reduced cue reactivity in the thalamus and ventral striatum compared to participants who relapsed.³⁴

The central hypothesis underlying this award is that brain circuitry associated with incentive salience valuation and executive control can be altered by treatment interventions and, consequently, serve as potential biomarkers of dependence reduction and cessation treatment outcomes. In a double-blind, randomized controlled trial, dependent smokers will be randomized to a 6-week VLNC cigarette intervention (N=50) or a 6-week normal nicotine content cigarette control condition (NNC; N=25). Participants will undergo fMRI scans at baseline, and 6-weeks to investigate the treatment-related modulation of brain circuitry involved in incentive salience valuation and executive control. Imaging tasks will assess the incentive salience of smoking cues and non-smoking rewards and executive function to identify changes in functional activity within, and effective connectivity between, known salience and executive control brain circuitry. A novel fMRI task using specialized odor presentation equipment and fMRI sequences will assess neural cue reactivity to smoke odors.

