7.0 Study Design and Procedures

7.1 Study Design

This is a two-arm, randomized, double-blind parallel group trial. Smokers will be randomly assigned to smoke very low nicotine content (VLNC) (n=50) or normal nicotine content (NNC) (n=25) SPECTRUM cigarettes for 6 weeks. Participants and study staff will be blind to the experimental cigarette allocation until the study is complete. The groups will be stratified by gender.

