7.4.3 Method for Assigning Subject to Treatment Groups

Participants will be randomized to one of two experimental conditions based on a blocked randomization sequence stratified by gender. A 2:1 randomization strategy will be used, resulting in 0.67 probability of being assigned to the very low nicotine cigarette, and a 0.33 probability of being assigned to the usual nicotine cigarette. The randomization key will be stored in REDCap and will be accessible only to unblinded study members and the faculty project mentor. The principal investigator will not have access to the code to ensure blinding.

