8.2 Sample size determination

Dependent smokers of low SES (n=75) will be recruited for the current study through the TCORS study call center (protocol #2213). Two-thirds of the sample (n=50) will be randomized to the VLNC group to maximize power for the within-subjects repeated measures analyses while still allowing for an analysis of between-subjects effects. There is not currently an accepted method for determining sample size a priori for repeated measures fMRI designs. With repeated measures behavioral data, to detect a medium effect size ($f=0.25$) with 80% power and a Type I error rate of .05, a sample size of 28 is required to detect within-subjects effects, 86 for between-subject effects, and 28 for within x between interactions. The estimate for detecting such effects with fMRI is likely somewhat higher; however, my mentors have found within-subject effects with similar tasks that will be used for this project with comparable sample sizes; smoking cue reactivity (n=22)⁶¹ card-guessing task (n=44)⁵, and the n-back task (n=33)⁶². Thus, we estimate that the current design will have adequate power to detect small to medium within-subjects effects and medium to large between-subjects effects. The design will serve as pilot data to determine sample size for future studies. TCORS found retention rates of 85% for their 18-week trial and a prior 6-week VLNC intervention found retention rates at 92%.⁴⁹ Retention for the proposed study will likely be higher given frequent contact with participants (3-week visit and two phone-check-ins); however, with a conservative estimate of 80% retention and adequate compliance, the final sample size (n=60) would still be adequately powered. We will recruit until we have 75 study completers. It is likely that participants that complete informed consent at the remote screening will be ineligible. Therefore, we expect around 90 participants to complete informed consent and 75 to complete the entire study.

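### Section 8.2's figure of 28 for the arm-by-time interaction does not describe the planned two-scan, 2:1 contrast, and adequate power at n=60 is not supported for a medium arm difference

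*Combined protocol and SAP*

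**What the plan says.** Section 8.2 sets its figures "to detect a medium effect size ($f=0.25$) with 80% power and a Type I error rate of .05", introduces them with "With repeated measures behavioral data", and gives the result that "a sample size of 28 is required to detect within-subjects effects, 86 for between-subject effects, and 28 for within x between interactions". It does not state the number of measurements, the correlation between them, the allocation behind the figures, or what f means for the interaction.

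The section explains the unequal arms: "Two-thirds of the sample (n=50) will be randomized to the VLNC group to maximize power for the within-subjects repeated measures analyses". It concludes that power is adequate for small to medium within-subjects effects and medium to large between-subjects effects, and that a final sample of 60, after 80% retention, would still have adequate power.

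Elsewhere the plan fixes the design. Section 1.1 words the hypotheses of Aims 1 and 2 as arm comparisons of change: "We hypothesize that, for the VLNC group compared to the normal nicotine content (NNC) group". Section 1.2 makes changes the primary endpoints. On scans, section 2.3 says "Participants will undergo fMRI scans at baseline, and 6-weeks". Section 7.1 plans 50 VLNC and 25 NNC participants, and section 7.4.3 says "A 2:1 randomization strategy will be used".

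**The concern.** The randomised comparison is the arm difference in change, which is the within x between interaction. The only sample size printed for it is 28. Beside a planned 75, or a fallback of 60, that figure suggests ample room.

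Two features make that impression unsafe. The figures seem to come from a different layout than the fMRI design. And one label, medium f=0.25, covers arm differences of quite different size in the between-subject and interaction figures. If this goes unnoticed, a null VLNC-NNC result could be taken as evidence of no effect when a moderate difference was likely to be missed. Later studies, which section 8.2 says will be sized from this one, would inherit the misreading.

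**Working it through.** **Inputs.** From section 8.2: f=0.25, 80% power, alpha 0.05, and 28/86/28. From sections 2.3, 7.1 and 7.4.3: two scans, 50/25, 2:1. The split 40/20 is section 8.2's 60 divided 2:1. The correlation r is not in the documents; it is back-solved below and then varied.

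**1. Reproduce 28/86/28.** Repeated-measures ANOVA, noncentral F, two equal groups, sphericity, m measurements:
- within and interaction: λ = f²Nm/(1−r), df = (m−1) and (N−2)(m−1)
- between: λ = f²Nm/(1+(m−1)r), df = 1 and N−2

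Smallest even N for 80% power (interaction / between; the within figure equals the interaction figure):

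| m | r=0.3 | r=0.5 | r=0.6 | r=0.7 |
|---|---|---|---|---|
| 2 | 46 / 84 | 34 / 98 | 28 / 104 | 22 / 110 |
| 3 | 38 / 70 | **28 / 86** | 24 / 96 | 18 / 104 |
| 4 | 32 / 62 | 24 / 82 | 20 / 90 | 16 / 100 |

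Of these settings, only m=3 with r=0.5 gives the printed figures.

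**2. Apply the planned layout.** With two scans and r=0.5 the figures are 34/98/34. For a fixed arm difference, 2:1 inflates the variance by (1/50+1/25)/(2/37.5) = 0.0600/0.0533 = 1.125. The interaction figure becomes 34 × 1.125 ≈ 38. Solving the between-subject case directly with λ multiplied by 1/1.125 gives 108 (72 and 36).

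**3. Translate f into an arm difference (raw SD units).**
- Between subjects, two groups: difference = 2f = 0.50 SD.
- Interaction, two scans: cell effects are ±0.25 SD, so each arm moves 2f in opposite directions. Difference in change = 4f = 1.00 SD.
- Interaction, three measurements, linear: 2a²/3 = 0.0625, a = 0.306, difference = 4a = 1.22 SD.
- Interaction, three measurements, step pattern (−2, 1, 1)b: 2b² = 0.0625, b = 0.177, difference = 6b = 1.06 SD.

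**4. Power for a 0.5 baseline SD difference in change** (assumed benchmark; one scalar outcome, two measurements, no baseline adjustment, two-sided 0.05). The SD of change is √(2(1−r)), which is 1 at r=0.5.
- 50/25: noncentrality 0.5/√(1/50+1/25) = 0.5/0.245 = 2.04; critical t on 73 df = 1.99; power 52.2%.
- 40/20: 0.5/√(1/40+1/20) = 0.5/0.274 = 1.83; critical t on 58 df = 2.00; power 43.5%.
- 50/25 at r=0.3 (SD of change 1.183): 40%. At r=0.7 (0.775): 74%.

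**5. Difference detectable with 80% power**, in baseline SD:
- 50/25: 0.695 at r=0.5; 0.695 × 0.775 = 0.54 at r=0.7; 0.695 × 1.183 = 0.82 at r=0.3.
- 40/20: 0.780 at r=0.5; 0.780 × 0.775 = 0.60 at r=0.7; 0.780 × 1.183 = 0.92 at r=0.3.

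**6. The section's own between-subject test.** At f=0.25 with its m=3, r=0.5 and equal arms, power is 74% at N=75 and 65% at N=60. Both are below 80%, as the printed 86 already implies.

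**The case against.** The case for leaving section 8.2 alone is substantial.

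- **The 28 is correct as defined.** At a 1.0 SD difference in change and r=0.5, power is 98% at 50/25 and 95% at 40/20. A reader might infer a calculation error; there is none. This stands.
- **0.5 SD is not in the documents.** It is borrowed from what f=0.25 means in the adjacent between-subject figure. The shortfall is conditional on that benchmark. This stands.
- **Section 8.2 draws no explicit conclusion about the interaction.** Its summary names only within- and between-subjects effects. If the arm difference in change is read as the between-subjects effect, the detectable 0.70 to 0.78 SD supports the upper part of medium to large. A reader might infer that the plan expressly claims power for the arm-by-time test; it does not. The impression comes from the 28 together with the statement about 60.
- **The section hedges.** It ties the figures to behavioural data, says fMRI probably needs somewhat more, says no accepted method exists, and describes the design as pilot data. But somewhat more than 28 still reads as well below 75, and the cited precedents (n=22, 44, 33) are for within-subject effects.
- **Some outcomes have three time points.** Aim 4 specifies three, and dependence questionnaires are repeated at the remote visits. Three measurements therefore suit those outcomes, but equal arms do not, and the implied difference is still 1.06 to 1.22 SD for step or linear patterns.
- **52% is one point in a range.** At r=0.8 power is 89%, and baseline adjustment at r=0.5 gives about 64%. This is why the range must accompany the figure.

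**Conclusion.** The point holds as a mismatch between the stated sizing and the planned contrast, of moderate severity. The 28 assumes three measurements and equal arms where the scans have two measurements and 2:1 allocation, and it corresponds to an arm difference in change of 1.0 SD or more. Adequate power at 60 is unsupported for a medium arm effect on section 8.2's own figure of 86, whatever benchmark is chosen for the interaction.

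The power figures (52%, range 40% to 74%, at 50/25; 43.5% at 40/20) rest on an assumed 0.5 baseline SD, an assumed correlation, a single scalar outcome, uncorrected two-sided alpha 0.05 and no baseline adjustment. They should not be read as the power of the primary analysis, because section 8.3 plans whole-brain and ROI testing. A reader might also infer that enrolment must rise to the 144 that 0.5 SD would need at 2:1. The documents do not commit to detecting 0.5 SD, so that does not follow.

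**What to change.** Reword section 8.2; enrolment, endpoints and analyses stay as they are.

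1. State the number of measurements, the assumed correlation, the 2:1 allocation and what f means for each effect.
2. Replace the 28 for the interaction with the detectable arm difference in change, in baseline (raw) SD units. Specify one pre-specified ROI or behavioural outcome, two measurements, no baseline adjustment, uncorrected two-sided alpha 0.05 and 80% power. At r=0.5 this is about 0.70 SD at 50/25 (0.54 to 0.82 for r=0.7 to 0.3) and 0.78 SD at 40/20 (0.60 to 0.92).
3. Add that power is lower after correction across ROIs or voxels. As an illustration, for 0.70 SD at 50/25 and r=0.5 it is about 59% at alpha 0.01 and 30% at 0.001.
4. Limit the adequacy claim at n=60 to within-subject effects and large arm differences.
5. Commit to reporting arm differences with confidence intervals, and say that a null result does not exclude differences below the detectable size.

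The cost is a less favourable power statement. No extra participants are needed.

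### Section 8.2 claims adequate power for small within-subjects effects, but calculates only for f = 0.25; at a conventional f = 0.10 and r = 0.5, power with 75 completers is 40% to 45%

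*Combined protocol and SAP*

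**What the plan says.** Section 8.2 sets its calculation in the context of repeated measures behavioural data. The stated target is "to detect a medium effect size ($f=0.25$) with 80% power and a Type I error rate of .05". The numbers it reports for this are 28 participants for the within-subjects test, 86 for the between-subjects test and 28 for their interaction. It adds that fMRI probably needs somewhat more, that no accepted a priori method exists for repeated measures fMRI, and that earlier studies of 22, 44 and 33 participants found within-subject effects with similar tasks. Its conclusion is: "Thus, we estimate that the current design will have adequate power to detect small to medium within-subjects effects". For between-subjects effects the claim is limited to medium and large ones.

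The same section gives within-subject power as the reason for placing 50 of 75 participants in the VLNC group. It also says that 60 participants, after 80% retention, would still be enough. On the imaging schedule, section 2.3 says: "Participants will undergo fMRI scans at baseline, and 6-weeks". Section 8.3 (Aim 1) plans paired comparisons of those two scans.

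**The concern.** The conclusion reaches below the effect for which anything was calculated. A sample size for f = 0.25 says nothing directly about small effects, because the required number grows roughly with 1/f². The earlier studies do not fill the gap: finding an effect with 22 to 44 people does not show power for a small one, and 8.2 reports no effect sizes from them.

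Within-subject sensitivity is the stated reason for the 2:1 allocation, and the study is meant to inform later sample sizes. A reader who trusts the sentence could take the absence of a detected change as evidence against a small effect when the design had less than an even chance of finding one.

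**Working it through.** **Inputs**
- From 8.2: alpha .05, 80% power, f = 0.25 called medium; required N of 28 (within), 86 (between) and 28 (interaction); 75 completers, 60 in the retention scenario, 50 in the VLNC group.
- Number of measurements m: two for the scans (2.3; 8.3, Aim 1). Questionnaires and out-of-scanner tasks are taken at three remote visits (7.2.3, 7.2.5, 7.2.7), so m = 3 fits the behavioural data.
- Assumed: small means f = 0.10, the usual companion to a medium of 0.25.
- Inferred: correlation r = 0.5 (step 1).

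**Formulas** (repeated-measures ANOVA, noncentral F, k groups)
- Within and interaction: λ = N·m·f²/(1 − r), with (m − 1) and (N − k)(m − 1) df.
- Between: λ = N·m·f²/(1 + (m − 1)r), with k − 1 and N − k df.

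**Step 1: reproduce the plan's figures** (m = 3, r = 0.5, k = 2)
- Within and interaction, N = 28: λ = 28 × 3 × 0.0625/0.5 = 10.5; df 2 and 52; power 81.2%.
- Between, N = 86: λ = 86 × 3 × 0.0625/2 = 8.06; df 1 and 84; power 80.1%.

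Over a grid of r = 0.3, 0.5, 0.7, 0.8 and m = 2, 3, 4, only this pair returns 28/86/28 (N rounded to equal groups). Two measurements with r = 0.5 return 34/98/34.

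**Step 2: same formula at f = 0.10, r = 0.5**

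With m = 3, λ = N × 3 × 0.01/0.5 = 0.06N; with m = 2, λ = 0.04N.

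| | m = 3: λ | power | m = 2: λ | power |
|---|---|---|---|---|
| n = 75 | 4.5 | 45.2% | 3.0 | 40.1% |
| n = 60 | 3.6 | 37.0% | 2.4 | 33.2% |
| VLNC, n = 50 | 3.0 | 31.3% | 2.0 | 28.4% |
| N for 80% | | 164 | | 200 |

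The m = 3 columns use the settings behind the plan's own numbers. The m = 2 columns change one input to match the scans. A two-sided paired t-test with a standardised difference of 0.2 gives the same 40.1%, 33.2% and 28.4%.

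**Step 3: vary r, at f = 0.10**

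| r | n = 75, m = 2 | n = 50, m = 2 | n = 75, m = 3 | n = 50, m = 3 |
|---|---|---|---|---|
| 0.3 | 30% | 22% | 34% | 23% |
| 0.5 | 40% | 28% | 45% | 31% |
| 0.7 | 60% | 43% | 68% | 49% |
| 0.8 | 77% | 59% | 85% | 67% |

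For 80% power, r must be about 0.81 (n = 75) or 0.88 (n = 50) with two scans, and about 0.77 or 0.85 with three measurements.

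**Step 4: what two scans can detect at r = 0.5**

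The smallest f with 80% power is 0.164 (n = 75), 0.184 (n = 60) and 0.202 (n = 50). Rounding down would miss the target: f = 0.16 at n = 75 gives 78.1%, and f = 0.20 at n = 50 gives 79.2%. Rounded up, the values are 0.17, 0.19 and 0.21. At f = 0.25, power is 99.0%, 96.8% and 93.4%.

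**The case against.** The plan gives no value for small. Its phrase can be read as the band between small and medium, and the detectable f of 0.164 at n = 75 (0.148 with three measurements) lies inside that band. On that reading the sentence is loose rather than false. This is fair, but the wording still includes small effects and nothing in 8.2 supports that end.

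The correlation is not stated either. Highly correlated behavioural measures could bring 75 completers above 80%: three measurements with r = 0.8 give 85%. That also stands, although the VLNC group would still have only 67%, and the plan's own figures point to 0.5.

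Section 8.2 is hedged. It says it is estimating, admits there is no accepted fMRI method and calls the design pilot data. These cautions argue against claiming adequate power for small effects; they do not support the claim. The same section expects fMRI to need more, and the figures above are for one test, before the whole-brain and ROI analyses of 8.3.

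Finally, the paired comparisons in 8.3 are across groups, so the VLNC-only figure is not the power of that test. It bears on the allocation rationale and on Aim 5, which concerns change within the VLNC group. Nothing in 8.3 commits the investigators to reading a null result as no change; that risk lies with the reader.

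**Conclusion.** The claim of adequate power for small within-subjects effects is unsupported and, under the settings that reproduce the plan's own sample sizes, not met: 45%, 37% and 31% for 75, 60 and 50 participants. With two scans the figures are lower still. This rests on f = 0.10 for small, r = 0.5, and a single test at alpha .05. With two scans the conclusion holds for r up to 0.8; with three measurements and r of about 0.77 or more it no longer holds for all 75 completers.

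Three stronger readings are tempting, and the documents do not support them. A reader might infer an arithmetic error in 8.2; there is none, since 28/86/28 reproduce exactly. A reader might take 40% and 28% as the result of the plan's own settings; those figures use two scans, whereas the plan's numbers imply three measurements. And a reader might conclude that the trial is too small for its within-subject aims in general; for a single test of a medium effect it is not.

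**What to change.** In section 8.2, replace the words on small to medium within-subjects effects with: *within-subject effects of about f = 0.17 or larger with 75 completers, 0.19 with 60, and 0.21 in the 50 VLNC participants (80% power, single test at alpha .05, two scans, assumed r = 0.5; lower after whole-brain or multiple-ROI correction).*

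Add that small effects (f = 0.10) are not powered under these assumptions, and qualify the statement about n = 60 in the same terms. State the number of measurements and the correlation behind 28/86/28, so that readers can see that those figures and the scan-based ones differ in m.

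The cost is a few sentences and a less favourable stated figure. Enrolment, allocation and analyses stay as they are.

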8.3 Statistical methods

Data Analysis. Images will be preprocessed using FSL, including registration to high resolution anatomical images and standard space, brain extraction, slice timing correction, spatial and temporal smoothing, intensity normalization, physiological noise correction, and motion correction for 6 motion parameters and artifacts identified via ICA-AROMA.⁶³ For task-based images, contrasts of the relevant conditions will be determined during first level analyses as described above and averaged across multiple runs for each participant.

Aim 1: Examine the longitudinal effect of VLNC cigarettes on changes in task-related functional neural activation within brain circuitry associated with incentive salience valuation and executive function.

Treatment-related within-subject and between-subject changes in BOLD activation during all fMRI tasks will be assessed in linear mixed-effects models using FSL software. Whole-brain analyses and ROI analyses based on pre-determined salience and executive control circuitry will be conducted. Paired t-tests will identify anatomical regions showing statistically significant differences from baseline to 6-week scans across groups.

Aim 2: Assess the longitudinal effect of VLNC cigarettes on changes in effective (directional) connectivity between incentive salience and executive control brain circuitry. Dynamic causal modeling (DCM) using SPM12 software will measure effective connectivity between ROIs in the incentive salience and executive control networks.⁶⁴ Specifically, DCM identifies models with task-specific increases in the dependence of the BOLD activity timecourses between a priori selected nodes and estimates directionality. We expect that the use of the VLNC cigarettes will strengthen the influence of the executive control over incentive salience circuitry during the smoking Go/NoGo and temporal discounting tasks. ROIs will be selected a priori for these analyses. Given the novelty of the odor cue reactivity task, active brain circuitry identified in Aim 1 will be included as nodes in the DCM model to test the hypothesis that non-smoking reward circuitry will exert an increasing influence over smoking salience circuitry. Connectivity estimates from the models will be included in a mixed-effects ANOVA to determine between-subjects and within-subject effects across the trial.

Aim 3: Establish measurable and objective neural outcomes of successful reductions in smoking dependence. FSL's Randomise one-sample t-test will be conducted on change scores to determine if changes in BOLD activity are associated with reductions in subjective markers of dependence (FTND, HONC, MNWS, QSU), cigarettes smoked per day, and quit intention and success. Changes in connectivity estimates will be correlated with changes in subjective and behavioral outcomes.

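### The Aim 1 paired t-tests appear to pool VLNC and NNC, so they cannot isolate a VLNC effect, and no VLNC-specific or group-by-time contrast is written for the mixed models beside them

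*Combined protocol and SAP*

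**What the plan says.** Section 7.1 assigns participants to "very low nicotine content (VLNC) (n=50) or normal nicotine content (NNC) (n=25) SPECTRUM cigarettes for 6 weeks", and section 7.4.3 confirms the ratio. Section 8.2 gives the reason: "Two-thirds of the sample (n=50) will be randomized to the VLNC group to maximize power for the within-subjects repeated measures analyses", while still allowing a between-subjects analysis. Section 2.3 fixes the imaging schedule: "Participants will undergo fMRI scans at baseline, and 6-weeks".

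Section 8.3 gives two analyses for Aim 1. The first is a set of linear mixed-effects models for treatment-related change, both within and between subjects; their terms and contrasts are not stated. The second finds the regions that changed: "Paired t-tests will identify anatomical regions showing statistically significant differences from baseline to 6-week scans across groups". The last two words are not defined.

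In section 1.1, every Aim 1 hypothesis is about VLNC compared with NNC. Section 1.2 makes change in neural reactivity to tobacco odor a primary endpoint.

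**The concern.** A paired t-test compares two scans of the same person and cannot compare independent arms. The quoted sentence therefore reads most naturally as one test on everyone with two scans. That raises two problems.

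The first is validity. A region can change between scans because of rescanning, habituation to the odors or practice on the tasks. A pooled test counts such change in the same way as an effect of the cigarettes, although the hypotheses concern a difference between arms. The result may also travel: for the odor task, section 8.3 takes the Aim 2 connectivity nodes from circuitry found active in Aim 1.

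The second is the link to the design. The plan accepts a loss of power for the arm comparison in order to place 50 participants in VLNC. The analysis that would use those 50 most directly is a test of change within VLNC, and Aim 1 does not write one down.

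**Working it through.** **Inputs.** Arms 50 and 25 (7.1). Fallback of 60 after 80% retention (8.2), taken here as 40 and 20. Two scans (2.3). Effect f=0.25, alpha .05, power 80% (8.2). The within-person correlation, the number of groups and the number of measurements behind the 8.2 figures are not stated.

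**Reproducing 8.2.** The plan says that "with 80% power and a Type I error rate of .05, a sample size of 28 is required to detect within-subjects effects", then "86 for between-subject effects, and 28 for within x between interactions". For repeated-measures ANOVA with k groups, m measurements and correlation r, the noncentrality is f²Nm/(1−r) for the within and interaction effects, and f²Nm/(1+(m−1)r) for the between effect. With k=2, m=3 and r=0.5:

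- within and interaction: N=28, noncentrality 0.0625×28×3/0.5 = 10.5
- between: N=86, noncentrality 0.0625×86×3/2 = 8.06

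These are the smallest equal-group sizes reaching 80%, so 28/86/28 is reproduced and r=0.5 is a fair inference. Section 8.2 offers these figures for behavioral data. With the two scans, the same settings give 34/98/34.

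**Effect in scan units.** With m=2, f=0.25 is a mean change of 0.5 SD. The SD of change is √(2(1−r)) = 1 at r=0.5, so the standardised change is 0.5. All power below is noncentral t, two-sided .05, for one test.

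**VLNC changes by 0.5 SD, NNC by 0.**

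- Pooled mean: (50×0.5 + 25×0)/75 = 0.333, one third below 0.5.
- Pooled SD: √(1 + (2/3)(1/3)(0.5²)) = 1.027. Standardised change: 0.333/1.027 = 0.324.
- Pooled power: noncentrality 0.324×√75 = 2.81, power 79%; at n=60, 0.324×√60 = 2.51, power 70%.
- VLNC only: 0.5×√50 = 3.54, power 93%; at n=40, 0.5×√40 = 3.16, power 87%.
- Smallest VLNC change detectable with 80% power: 0.40 SD (VLNC only, n=50) against 0.51 (pooled, n=75); with 40 and 20 retained, 0.45 against 0.57.

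**Dependence on NNC.** VLNC change stays at 0.5 SD. VLNC-only power stays at 93% (n=50) and 87% (n=40).

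| NNC change (SD) | Pooled mean | Pooled power, n=75 | Pooled power, n=60 |
|---|---|---|---|
| −0.1 | 0.300 | 69% | 59% |
| 0 | 0.333 | 79% | 70% |
| 0.1 | 0.367 | 87% | 78% |
| 0.25 | 0.417 | 94% | 88% |
| 0.5 | 0.500 | 99% | 97% |

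**No treatment effect, both arms shift by an assumed 0.3 SD.** Pooled, n=75: 0.3×√75 = 2.60, significant 73% of the time. VLNC only, n=50: 0.3×√50 = 2.12, significant 55% of the time. For a shift of 0.2 SD the rates are 40% and 28%.

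**What 2:1 does at N=75, against 38/37** (VLNC 0.5 SD, NNC 0).

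- Pooled test: 79% against 56%, because the dilution is one third rather than about one half.
- VLNC-only test: 93% (n=50) against 85% (n=38).
- Arm difference in change of 0.5 SD: 0.5/√(1/50+1/25) = 2.04, power 52%, against 57%.

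**The case against.** A reader might infer more than the documents support, in four ways.

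- *That the pooled t-test is the only within-subject analysis in Aim 1.* It is not. The mixed models in the same paragraph are assigned treatment-related within-subject change and could carry a VLNC-specific contrast. What stands is that no such contrast is written.
- *That the 2:1 split does nothing for the pooled test.* It leaves the number of observations at 75, but it raises that test's power from 56% to 79% in the scenario above. The rationale in 8.2 is also worded for within-subject analyses in general. Aim 5 studies within-subject change in the VLNC group, and Aim 2 has its own within-subject effects. The allocation does not hang on one sentence.
- *That the signal is always diluted by one third.* This needs zero change in NNC, which the documents do not state. If NNC moves 25% or 50% as far as VLNC, the dilution is 25% or 17%, and at about half the pooled test has caught up.
- *That a VLNC-only test would cure the validity problem.* It would not: it is significant 55% of the time under the same common shift.

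Two further points are fair. The plan intends to recruit until 75 complete, and there the pooled power of 79% is barely under the 80% benchmark; the 70% belongs to the fallback, about which 8.2 says "the final sample size (n=60) would still be adequately powered". And pooling is the natural reading of an undefined phrase, not the only possible one. Neither point gives the paired t-test the ability to isolate a VLNC effect.

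**Conclusion.** The point holds in a limited form. As worded, the test that is to identify changed regions appears to pool the arms, so its result cannot be attributed to VLNC cigarettes. The two contrasts that would answer the hypotheses and use the allocation as 8.2 intends are not written. This is a weakness in a stated analysis. It is not evidence that the allocation is wrong or that Aim 1 lacks a suitable model.

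The validity problem is the weightier half and does not depend on what NNC does in the power scenario; its size (73% at n=75) depends on the assumed 0.3 SD shift. The power loss, 79% against 93% at full size and 70% against 87% at the fallback, rests on no NNC change, equal SD of change in the arms, an inferred correlation of 0.5, equal retention for the fallback, and one uncorrected test. Whole-brain correction would lower all these figures, so they describe relative performance and are not power for the imaging analysis. The change should be made, and it is cheap.

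**What to change.** In section 8.3, Aim 1, replace the pooled paired t-tests with two written contrasts:

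1. The group-by-time contrast (VLNC change minus NNC change) from the mixed model already planned, as the basis for every statement about treatment-related change.
2. A VLNC-only baseline-to-week-6 contrast, named as the within-subject analysis that 8.2 refers to. Report it beside the NNC change, both with confidence intervals. Do not read it as a treatment effect on its own, and do not infer an effect from one arm being significant and the other not.

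If the sponsor meant something other than pooling, the phrase should be defined.

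In section 8.2, tie the within-subject power statement to the VLNC group. Label any figure there as a single-test approximation for behavioral data and state its assumed correlation; the 93% and 87% above should not be entered as fMRI power.

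The cost is wording in two sections and a different group-level design file. No new data and no change to allocation or enrolment are needed. The downside is small: if both arms change equally by 0.5 SD, the VLNC-only test has 93% power (n=50) where the pooled test would have 99% (n=75).
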